- dabigatran (Pradaxa) – when necessary utilize aPTT or ECT to assess for anticoagulant activity.
- apixaban (Eliquis) - no need to monitor anticoagulation effect, in cases of suspected non-compliance, or in other unusual circumstances, assessment of the anticoagulant effect of apixaban may be appropriate. The Chromogenic anti-Factor Xa chromogenic assays are preferable to the PT test because they yield more accurate results but may be used in emergency situations when an anti-Factor Xa assay is not available.
- Rivaroxaban (Xarelto) - routine measurement of Rivaroxaban plasma levels or its pharmacodynamics effects is not required or recommended. The Chromogenic anti-

Factor Xa chromogenic assays are preferable to the PT test because they yield more accurate results but, may be used in emergency situations when an anti-Factor Xa assay is not available.

5.3.5 Post EP Procedure (2nd Blanking Period) Antiarrhythmic Medication Therapy – AAD Management and Recommended Guideline

Following the EP ablation procedure, a subject may be continued on an AAD for up to 90 days (which shall be called the Post Endocardial EP ablation procedure blanking period). If the subject is in sinus rhythm at the 3-month post endocardial EP ablation procedure, the subject's AAD therapy will be discontinued. If the atrial arrhythmia returns, the subject may be returned to AAD therapy utilizing an AAD that the subject previously failed at a dose not exceeding those previously failed from baseline. The 3-month period between the blanking period and the 6-month visit will be utilized for AAD medication optimization. An arrhythmia will not be considered an effectiveness failure during this time period. AAD medication must be optimized prior to the 6-month visit, at which time any arrhythmias will be counted towards the effectiveness endpoints. At the 6-month visit, if the subject is in sinus rhythm on a previously failed AAD at a dose not exceeding previously failed, the subject may remain on the AAD.

Re-ablation to treat Atrial Fibrillation, Atrial Tachycardia, and Atrial Flutter following Endocardial EP Catheter Ablation

Subjects that experience atrial fibrillation, atrial tachycardia, or atrial flutter may be treated with a catheter ablation if deemed medically necessary following the Endocardial EP Ablation Procedure.

Second Blanking Period Catheter Ablation

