7.13 Visit 10 – 6 Month Post Endocardial EP Ablation Procedure

A follow-up evaluation will be scheduled for **6 months (180 days ± 30 days)** post Endocardial EP Ablation Procedure. The following will be conducted and/or obtained at the 6 Month Visit:

- Targeted Physical Examination
- Weight
- Blood pressure and Heart Rate
- NYHA Class
- RBC, WBC, HGB, HCT, Platelets, BUN (Urea), Creatinine
- Heart Rhythm Assessment - 30 second ECG
- 24-Hour Continuous ECG Monitoring/ Arrhythmia Monitoring - Holter or ZioTM Patch
- Concomitant procedures to treat arrhythmia (i.e., cardioversion for subjects in atrial fibrillation), performed at physician discretion
- Medications Review
- Anticoagulation Testing in accordance with institutional SOC (e.g., INR for subjects on warfarin or aPTT or ECT if on dabigatran)
- Adverse Event Assessment
- Symptom-driven event monitoring will begin at this visit. Subjects will receive a symptom-driven monitor at this visit to capture any symptoms of atrial fibrillation. Site will instruct the subject on use of the monitor along with how to upload data to core laboratory for interpretation of rhythm.
- CT/MR imaging only if subject exhibits symptoms suggestive of pulmonary vein stenosis. (Note: Use same imaging technique performed at baseline PV imaging to the extent possible.)

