2.1.1 Primary Effectiveness Endpoint

The primary effectiveness endpoint is freedom from any documented AF, atrial flutter, or atrial tachycardia lasting >30 seconds in duration through the 12-month follow-up visit in the absence of Class I or III AADs (with the exception of previously failed AADs at doses not exceeding those previously failed).

Any arrhythmia that occurs within the blanking period or the AAD Optimization period will not be considered a failure (Visit 5 up to Visit 10). The rhythm status used for evaluation of this endpoint will be derived from regularly scheduled monitoring (i.e. Holter, Zio™-Patch, or 30 second ECG) as well as any symptom driven monitoring that is performed.

The following scenarios shall constitute a failure of the primary effectiveness endpoint:

1. Any documented AF, atrial flutter, or atrial tachycardia lasting >30 seconds duration that occurs at any time beginning at the 6-month visit and through the 12-month visit. These will be

Statistical Analysis Plan		Page 6 of 22
Sponsor	Study	Version
AtriCure	DEEP Pivotal Study	Version 2.0

documented on any Core Lab – ECG form with a time interval of “6 Month Post Endocardial” or “12 Month Post Endocardial”.

2. Any previously failed class I or III AAD administered at a dose higher than baseline and between the 6-month visit date plus one day and the 12-month visit date.
3. Any newly introduced class I or III AAD usage beginning at the 6-month visit date plus one day and through the 12-month visit date.
4. DC cardioversion for AF, atrial flutter, or atrial tachycardia that takes place at any time beginning at the 6-month visit date and ending at the 12-month visit date.
5. Catheter ablation or surgical treatment for AF, atrial flutter, atrial tachycardia that takes place at any time beginning at the 3-month visit date and ending at the 12-month visit date.
6. Two or more repeat catheter ablations within the 2nd blanking period.
7. The use of a non-AtriCure study device for creation of any lesions during the surgical epicardial ablation procedure.

For the purposes of this study, atrioventricular nodal reentrant tachycardia (AVNRT), inappropriate sinus tachycardia, and Wolff–Parkinson–White syndrome (WPW) will not be considered procedure failures.

For this study, AtriCure defines failure of an antiarrhythmic drug (AAD) to include ineffectiveness or intolerance of the AAD.

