5.1.3 Visit Windows

Unless otherwise specified, visit based assessments will be analyzed for each analysis time point according to the nominal visit entered in the Case Report Form (CRF) regardless of if it is out of window.

Statistical Analysis Plan		Page 11 of 22
Sponsor	Study	Version
AtriCure	DEEP Pivotal Study	Version 2.0

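### Antiarrhythmic drug and cardioversion failures are counted only from the attended 6-month visit, so a visit after day 210 excuses later events and a missed visit leaves the window with no start date

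*SAP*

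**What the plan says.** SAP 2.1.1 lists seven ways to fail the primary effectiveness endpoint. Three of them are timed by attended visit dates:

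- Scenario 2, a previously failed AAD at a higher dose: "between the 6-month visit date plus one day and the 12-month visit date".
- Scenario 3: "Any newly introduced class I or III AAD usage beginning at the 6-month visit date plus one day and through the 12-month visit date".
- Scenario 4, cardioversion: "takes place at any time beginning at the 6-month visit date and ending at the 12-month visit date".

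Scenario 1, recurrent arrhythmia, works differently. It is "documented on any Core Lab – ECG form with a time interval of" 6 or 12 months, so it depends on a form label and not on a visit date.

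Protocol 7.13 schedules Visit 10 at "6 months (180 days ± 30 days") after the endocardial procedure, that is, days 150 to 210. Protocol 7.14 puts Visit 11 on days 365 to 395. Protocol 5.3.5 gives the purpose of the interval before Visit 10: "The 3-month period between the blanking period and the 6-month visit will be utilized for AAD medication optimization". SAP 5.1.3 analyses visit-based assessments "according to the nominal visit entered in the Case Report Form (CRF) regardless of if it is out of window".

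Protocol 3.1 uses the same visit-to-visit period as the SAP. Neither document gives a fallback date for a subject with no Visit 10.

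**The concern.** Whether a given cardioversion or drug course is a primary failure depends on when, or whether, the subject attended Visit 10. Inside the permitted window this follows from a visit-based endpoint. Outside it, nothing limits the effect. A late visit lengthens the excused period past the protocol's own limit. A missed visit leaves the programmer to choose a start date, possibly with outcome data in view.

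The primary test compares one proportion with a fixed 60%. There is no control arm in which the same slippage would occur and cancel out, so any net shift towards success goes straight into the test.

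**Working it through.** **The plan's own figure.** Protocol 9.3 assumes 70% success against 60%, one-sided alpha 0.025 and 80% power, and gives N = 182. The uncorrected formula reproduces it: [(1.960 × √(0.60 × 0.40) + 0.842 × √(0.70 × 0.30)) / 0.10]² = 181.1, rounded up to 182. (With the continuity correction that the protocol names, the result is 191.0, rounded up to 192. That is a separate matter.)

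**What the visit date does to the window.** The 2nd blanking period is 90 days. The optimization period is the Visit 10 day minus 90. The counted period, taking Visit 11 on day 365, is 365 minus the Visit 10 day.

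| Visit 10 day | Status | Optimization (days) | Counted to day 365 (days) |
|---|---|---|---|
| 150 | in window | 60 | 215 |
| 180 | target | 90 | 185 |
| 210 | upper limit | 120 | 155 |
| 240 | late | 150 | 125 |
| 260 | late | 170 | 105 |

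**Late visit.** Take a cardioversion on day 230. With Visit 10 on day 210 it is a failure. With Visit 10 on day 260 it falls before the window opens and is not counted. For AADs the loss is narrower. A course that ended before the late visit drops out. Ongoing use still counts, unless scenario 3 is read as referring to the drug's start date.

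**Missed visit.** Take a subject with no Visit 10, a cardioversion on day 250, and sinus rhythm at Visit 11.

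1. SAP 5.2: the primary mITT population needs one visit after the 2nd blanking period with non-missing effectiveness data. Visit 11 is enough, so the subject is included.
2. SAP 2.1.1: scenario 4 has no start date to compare with day 250.
3. SAP 5.6.1.1: a subject with no failure recorded between the two visits is a success.
4. SAP 5.3: the worst-case rule applies only when 12-month test data are absent, and this subject has them. Last observation carried forward fills in a missing test result but does not supply a window start.
5. Scenario 1 is not a dependable backstop. A subject back in sinus rhythm may have nothing on the labelled core-lab forms, and Protocol 7.13 hands out the symptom-driven monitor at Visit 10 itself.

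**Illustration of the size.** Inputs from the documents: null rate 60%, one-sided alpha 0.025, and N = 182 (required) or 220 (maximum treated). Assumptions: the true success rate is exactly 60%, and a net share m of all subjects is wrongly scored as success. The exact binomial test passes at 123 of 182 or 147 of 220. The uncorrected one-sided chi-squared test gives the same pass marks, so it does not matter here that Protocol 9.7.1 names one test and SAP 5.6.1.1 the other. The true one-sided error is P(X ≥ pass mark) with X binomial(N, 0.60 + m):

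| m | N = 182 | N = 220 |
|---|---|---|
| 0 | 2.1% | 2.2% |
| 1% | 3.9% | 4.4% |
| 2% | 6.9% | 7.9% |
| 3% | 11.4% | 13.5% |

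One per cent of 220 is 2.2 subjects. One route to m = 1%: with 40% true failures, 10% of subjects miss Visit 10, and 25% of failures show only as AAD use or cardioversion, so 0.40 × 0.10 × 0.25 = 0.010. With the same 25% and a missed-visit rate of 1%, 2% or 5%, m is 0.1%, 0.2% or 0.5%, and the error at N = 220 is 2.4%, 2.5% or 3.1%.

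**The case against.** The strongest reply is that the protocol itself defines the failure period by visits. Protocol 3.1, 9.2.1 and 9.7.1 all run from the 6-month to the 12-month visit, and 5.3.5 requires AADs to be optimized before the 6-month visit. The SAP applies that definition. This stands for every visit inside days 150 to 210, including early visits, which lengthen the counted period and add failures.

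A reader might go further and infer that the whole spread of windows is an error: 155 days (365 − 210) to 245 days (395 − 150). At a constant failure rate giving 70% over 185 days, that would move success between 0.70^(155/185) = 74.2% and 0.70^(245/185) = 62.4%. The documents do not support this. The spread is the protocol's own design, and the calculation moves every failure although scenario 1 is keyed to form labels. If an assumed 25% of the failure rate depends on visit dates, the range is 0.70^(177.5/185) = 71.0% to 0.70^(200/185) = 68.0%, and even that needs every subject at the same extreme.

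Two other stronger readings also fail. A missed Visit 10 does not certainly produce a success. Success is the default, but if a blank date were programmed as earlier than everything, cardioversions inside the blanking period would become failures. Nor is a missing Visit 11 unhandled: SAP 5.3 gives four rules for absent 12-month data, and only the literal closing date is unstated.

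It is also true that the documents give no rate of missed or late visits, so the error figures are illustrations, and that with few missed visits the effect is negligible.

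What the reply does not answer is the part outside the window. The protocol sets an upper limit of day 210, SAP 5.1.3 removes it, and nothing covers a subject who skips Visit 10.

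**Conclusion.** The point holds for Visit 10 after day 210 and for Visit 10 missed. A late visit excuses cardioversions, and AAD courses already ended, that occur beyond the protocol's own window. A missed visit leaves scenarios 2 to 4 without a start date, success is the default, and the worst-case analysis does not reclassify a subject who has 12-month data.

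The gap is certain from the text; its size is not. The move from 2.2% to 4.4% rests on a true rate of 60%, N = 220, and an assumed net 1% misclassified as success. The change should be made because it closes an undefined case in the primary endpoint at little cost, not because a large bias has been shown.

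**What to change.** In SAP 2.1.1, for scenarios 2 to 4:

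- **Start:** the Visit 10 date (plus one day for AADs, as now) or day 210 after the endocardial procedure, whichever is earlier; day 210 if Visit 10 is missed.
- **End:** the Visit 11 date, or day 395 if Visit 11 is missed. The SAP 5.3 rules for missing 12-month data stay unchanged.
- **Subjects without an endocardial procedure (ITT analysis):** count the days from the surgical procedure, as Protocol 9.2.1 does.
- **Scenario 1:** leave it keyed to the core-lab form labels.

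The rule should name the endocardial procedure as its day 0, because SAP 5.1.2 counts study days from an index procedure without saying which stage. Carry the same wording into Protocol 3.1.

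The cost is two derived dates per subject from data already collected, alignment of the protocol's endpoint wording, and a few more events counted as failures. Scoring for visits held inside the window does not change, so early visits are treated as they are now.

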3.0 STUDY ENDPOINTS

3.1 Primary Effectiveness Endpoint

The primary effectiveness endpoint is freedom from any documented AF, atrial flutter, or atrial tachycardia lasting >30 seconds duration through the 12-month follow-up visit in the absence of Class I or III AADs (with the exception of previously failed AADs at doses not exceeding those previously failed).

Any arrhythmia that occurs within the blanking period or during the “AAD Optimization Period” visit will not be considered a failure (Visit 5 up to Visit 10). The rhythm status used for evaluation of this endpoint shall be derived from regularly scheduled monitoring (i.e., Holter, Zio™ Patch, or 30 second ECG), as well as any symptom driven monitoring that is performed.

The following scenarios shall constitute a failure of the primary effectiveness endpoint:

1. Any documented AF, atrial flutter, or atrial tachycardia lasting >30 seconds duration) that occurs at any time beginning at the 6-month visit and through the 12-month visit.
2. Any previously failed class I or III AAD administered at a dose higher than baseline and between the 6-month visit and the 12-month visit.
3. Any newly introduced class I or III AAD usage beginning at the 6-month visit through the 12-month visit.
4. DC cardioversion for AF, atrial flutter, or atrial tachycardia that takes place at any time beginning at the 6-month visit through the 12-month visit.
5. Catheter ablation or surgical treatment for AF, atrial flutter, atrial tachycardia that takes place at any time beginning at the 3-month visit and ending at the 12-month visit.
6. Two or more repeat catheter ablations within the 2nd blanking period
7. The use of a non-study device for creation of any lesions during the surgical epicardial ablation procedure

For the purposes of this study, atrioventricular nodal reentrant tachycardia (AVNRT), inappropriate sinus tachycardia, and Wolff–Parkinson–White syndrome (WPW) will not be considered procedure failures.

For this study, AtriCure defines failure of an antiarrhythmic drug (AAD) to include ineffectiveness or intolerance of the AAD.

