3.6 Blanking Periods

It is traditional to have a "blanking period" following any intervention for cardiac arrhythmias. During the blanking period, neither a recurrence of the pre-interventional arrhythmia that was treated nor a new arrhythmia resulting from the intervention itself is considered to represent a "failure" of the interventional procedure. The traditional blanking period for the interventional treatment of atrial fibrillation has been 90 days.

There are two reasons for suggesting that each blanking period last for approximately 90 days following the specific intervention:

- To allow the surgical lesions and later the catheter ablation lesions to fully heal; and
- To allow the electrophysiological characteristics of the atrium, such as local refractory periods, conduction velocity, etc., to return to their pre-intervention baselines. Even in patients who have a cut-and-sew Maze procedure for atrial fibrillation, in which "healing" of the lesions is not an issue, the blanking period is still 90 days because of the need to allow the atrium to heal completely from the surgery.

Since the proposed DEEP procedure requires two individual interventional procedures, two separate blanking periods are included in this protocol. The 1st blanking period is from the time of the Epicardial Surgical Ablation Procedure through the Endocardial EP Ablation Procedure (which is approximately 90 days). The 2nd blanking period is 90 days post Endocardial EP Ablation Procedure. During these intervals, the effectiveness of the Epicardial/Endocardial Ablation Procedure is not evaluated for arrhythmia recurrence and re-intervention to address atrial dysrhythmia may be performed.

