7.12 Visit 9 – 3 Month Post Endocardial EP Ablation Procedure

A follow-up evaluation will be scheduled for **3 months (90 days + 14 days)** post EP Endocardial Ablation Procedure. The following will be conducted and/or obtained be performed at the 3 Month Visit:

- Targeted Physical Examination
- Weight
- Blood pressure and Heart Rate
- NYHA Class
- RBC, WBC, HGB, HCT, Platelets, BUN (Urea), Creatinine
- Heart Rhythm Assessment - 30 second ECG
- Concomitant procedures to treat arrhythmia (i.e., cardioversion for subjects in atrial fibrillation), performed at physician discretion
- Medication Review
- Anticoagulation Testing in accordance with institutional SOC (e.g., INR for subjects on warfarin or aPTT or ECT if on dabigatran)
- Adverse Event Assessment
- Begin AAD optimization period if patient is in AF.

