5.2 Analysis Populations

Intent to treat patient population (ITT): The ITT subject population will include all subjects who have met all inclusion/exclusion criteria and on whom a procedure was attempted (defined as a subject who underwent induction of anesthesia).

Modified intent to treat patient population (mITT): The mITT subject population will include all subjects who attempted the Epicardial Procedure (defined as a subject who underwent induction of anesthesia) and have at least one post-procedure follow-up visit after the 2nd Blanking Period (with the 2nd blanking period defined as the 90-days post Endocardial Ablation Procedure) with non-missing primary effectiveness data.

Safety Population: The safety population will include all enrolled subjects that undergo induction of anesthesia.

Per protocol patient population (PP): The PP patient population will include all subjects who complete both the Epicardial Surgical Ablation Procedure and Endocardial EP Ablation Procedure.

AtriClip Effectiveness population: The AtriClip effectiveness population will include all ITT subjects for whom an attempt (entrance of the AtriClip into the chest wall) is made to place an AtriClip device.

The primary effectiveness analysis will utilize the mITT patient population as defined in this statistical analysis plan. The analysis will be repeated on the ITT and PP patient populations as supportive analyses. Secondary effectiveness analyses will be conducted on the mITT, the ITT and the PP patient populations. All safety analyses will utilize the safety population.

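### Failure scenario 5 starts at the 3-month visit date although blanking ends at day 90, so a single repeat ablation between the two meets no failure scenario

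*SAP*

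**What the plan says.** **Scenario 5.** The SAP (2.1.1) counts as a failure "Catheter ablation or surgical treatment for AF, atrial flutter, atrial tachycardia that takes place at any time beginning at the 3-month visit date"; the full window is "beginning at the 3-month visit date and ending at the 12-month visit date". The protocol (synopsis and 3.1) uses the same visit anchor without the word date: "beginning at the 3-month visit and ending at the 12-month visit".

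**Scenario 6.** The only other rule on repeat catheter ablation is "Two or more repeat catheter ablations within the 2nd blanking period" (SAP 2.1.1).

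**Length of the 2nd blanking period.** Protocol 3.6: "The 2nd blanking period is 90 days post Endocardial EP Ablation Procedure". The SAP agrees in its mITT definition (5.2): "with the 2nd blanking period defined as the 90-days post Endocardial Ablation Procedure".

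**Timing of the 3-month visit (Visit 9).** Protocol 7.12 sets "3 months (90 days + 14 days"), which is day 90 to day 104 after the endocardial procedure.

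**Re-intervention.** Protocol 5.3.5 says that an ablation inside the blanking period is not a failure, and it allows re-intervention at any time in the study if medically necessary.

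**Success rule.** Protocol 9.7.1 and SAP 5.6.1.1 call a subject a success if no failure was recorded from the 6-month visit through the 12-month visit.

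**The concern.** One boundary is fixed by the calendar and the other by attendance. Two subjects ablated on day 95 would be scored differently if one attended Visit 9 on day 92 and the other on day 100: the first fails under scenario 5, the second does not. Nothing about their outcomes differs.

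Scenario 5 starts about three months before scenarios 1 to 4, so the plan evidently means re-ablation after blanking to count as treatment failure. The arrhythmia that prompts such an ablation is itself excused until Visit 10, so it does not catch the subject either. The endpoint is primary and is tested in a single arm against a fixed 60%, where a few reclassified subjects change the operating characteristics. A start date that depends on attendance also leaves the programmer to improvise when Visit 9 was never held.

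**Working it through.** **1. Which scenario catches a single repeat ablation after day 90 and before Visit 9?** Day 0 is the endocardial procedure; blanking is days 1 to 90.

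- Scenario 1 (arrhythmia), scenarios 2 and 3 (antiarrhythmic drugs) and scenario 4 (cardioversion) start at the 6-month visit or the day after: no.
- Scenario 5 starts at the Visit 9 date: no.
- Scenario 6 needs at least two repeat ablations inside blanking: no.
- Scenario 7 concerns the surgical procedure only: no.

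Two ablations in the gap, or one in blanking and one in the gap (for example days 60 and 100 with Visit 9 on day 104), also meet neither scenario 5 nor scenario 6.

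**2. Length of the gap.** For Visit 9 on day V, with V at least 91, the uncounted days are 91 to V − 1, so the gap is V − 91 days.

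| Visit 9 | Uncounted days | Length |
|---|---|---|
| day 90 or 91 | none | 0 |
| day 97 | 91–96 | 97 − 91 = 6 |
| day 104 (last in window) | 91–103 | 104 − 91 = 13 |
| day 120 (late) | 91–119 | 120 − 91 = 29 |
| missed | no start date defined | read literally, scenario 5 never applies |

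An in-window visit on any of days 92 to 104 is enough to open the gap.

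**3. Reverse case.** With Visit 9 held early, say on day 80, a single ablation on day 85 lies inside blanking, where Protocol 5.3.5 says it is not a failure, yet scenario 5 scores it as one.

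**4. The plan's own sample size, as context.** Inputs from Protocol 9.3: null 0.60, expected 0.70, one-sided alpha 0.025, power 80%.

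n = [(1.960·√(0.6·0.4) + 0.842·√(0.7·0.3)) / 0.10]² = 181.1, rounded up to 182.

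This reproduces the stated 182, but without the continuity correction that the section names; with it, n is 191.003, rounded up to 192. That is a separate matter, and the present point does not depend on it.

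**5. Size of the effect.** The documents give no rate of repeat ablation, so the number m of subjects counted as successes only because of the gap is an assumption. Let X ~ Binomial(N, 0.60) be the number of true successes and c the smallest count that passes at one-sided 0.025. The exact test (Protocol 9.7.1) and the uncorrected chi-squared test (SAP 5.6.1.1) give the same c here. The chance of passing is P(X ≥ c − m).

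| N | c | m = 0 | m = 1 | m = 2 |
|---|---|---|---|---|
| 182 (stated requirement) | 123 | 2.1% | 3.0% | 4.3% |
| 200 (illustrative) | 134 | 2.5% | 3.5% | 4.7% |
| 220 (maximum treated) | 147 | 2.2% | 3.1% | 4.2% |

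**6. After the change.** With scenario 5 starting on day 91 there are no uncounted days for any Visit 9 date, including a missed visit. The sample size is unaffected.

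**7. Success rule beside scenario 5.** Scenario 5 counts ablations from month 3. The success rule in Protocol 9.7.1 and SAP 5.6.1.1 looks only at failures recorded from the 6-month visit. Read literally, it drops every scenario 5 ablation between months 3 and 6, a longer stretch than the gap above.

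**The case against.** The strongest reply is that Visit 9 is meant to be the hand-over from blanking to drug optimization. Protocol 7.12 and the schedule of assessments start optimization there, and Protocol 3.6 speaks of each blanking period as lasting about 90 days. On that reading a single ablation before Visit 9 is the one extra procedure that Protocol 7.9 allows, and a second one falls under scenario 6. This makes loose drafting a plausible origin. It does not close the gap: both documents also define the 2nd blanking period as 90 days, neither says that it runs to Visit 9, and a missed Visit 9 would still leave no boundary.

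The limits on size also stand. A gap ablation gives no immunity, because the subject still faces scenarios 1 to 4 from the 6-month visit and scenario 5 from Visit 9. The in-window gap is 13 days at most.

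Three stronger readings are tempting and are not supported:

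- A reader might infer a large inflation of the error rate. That needs several subjects ablated in a short interval, none of whom fails later, and the documents offer no figure for either.
- A reader might infer that sites could remove a failure by holding the visit after the ablation. The wording permits that result, but nothing in the documents suggests such conduct.
- A reader might take SAP 5.1.3, which keeps the nominal visit "regardless of if it is out of window", as a cause of the gap. That rule governs visit-based assessments; a repeat ablation is a dated event. The out-of-window extension follows from the words visit date in SAP 2.1.1 alone.

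**Conclusion.** The point holds as a narrow defect in a primary endpoint rule. A single repeat ablation after day 90 and before Visit 9 meets no failure scenario. The gap is 1 to 13 days for an in-window visit on days 92 to 104 and longer for a late visit, and the start of scenario 5 is undefined if the visit is missed. In those cases the effect favours the device. It is not one-sided in principle, because an early Visit 9 turns a blanking-period ablation into a failure.

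The size rests on an assumption. If one or two subjects are credited only through the gap and do not fail later, the chance of passing at a true 60% rises from 2.1% to 3.0% or 4.3% at 182 subjects, and from 2.5% to 3.5% or 4.7% at 200. If nobody is ablated in the gap, there is no numerical effect, but the rule is still incomplete. The success rule that starts at month 6 conflicts with scenario 5 over a longer period and belongs in the same correction.

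**What to change.** 1. In SAP 2.1.1 and the matching protocol text (synopsis and 3.1), start scenario 5 on day 91 after the index endocardial procedure, whatever the date of Visit 9 and whether or not it took place.
2. For subjects who never have the endocardial procedure, start scenario 5 at the end of the 3-month blanking period measured from surgery, as Protocol 9.2.1 already does for their follow-up. A day-91 rule tied only to the endocardial procedure would leave these ITT subjects without an anchor.
3. Reword the success rule in Protocol 9.7.1 and SAP 5.6.1.1 so that scenario 5 failures between the end of blanking and month 6 count. The missing-data sections (Protocol 9.9, SAP 5.3) use the same 6-to-12-month wording and should follow.

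The cost is a few phrases in each document, with no change to data collection or sample size. SAP section 6 already provides for amendment before analysis. The downside for the sponsor is possibly one or two more failures.
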